6.1.1 Serious Adverse Event (SAE) Definition

A serious adverse event is one that at any dose (including overdose):

- Results in death
- Is life-threatening¹
- Requires inpatient hospitalization or prolongation of existing hospitalization
- Results in persistent or significant disability or incapacity²
- Is a congenital anomaly or birth defect

- Is an important medical event³
- Pregnancy
- 1. "Life-threatening" means that the subject was at immediate risk of death at the time of the serious adverse event; it does not refer to a serious adverse event that hypothetically might have caused death if it were more severe.
- ^{2.} "Persistent or significant disability or incapacity" means that there is a substantial disruption of a person's ability to carry out normal life functions.
- 3. Medical and scientific judgment should be exercised in deciding whether expedited reporting is appropriate in situations where none of the outcomes listed above occurred. Important medical events that may not be immediately life-threatening or result in death or hospitalization but may jeopardize the patient or may require intervention to prevent one of the other outcomes listed in the definition above should also usually be considered serious. Examples of such events include allergic bronchospasm requiring intensive treatment in an emergency room or at home, blood dyscrasias or convulsions that do not result in inpatient hospitalization, or the development of drug dependency or drug abuse. A new diagnosis of cancer during the course of a treatment should be considered as medically important.

6.2 Adverse Event Reporting

Protocol Chair

The Protocol Chair is ultimately responsible for the required reporting of all adverse events.

Coordinating Center

The Coordinating Center is the central location for the collection and maintenance of documentation of adverse events and is responsible for submitting adverse event reports to the Protocol Chair promptly. The Coordinating Center will maintain documentation of all adverse event reports for each participating site. Adverse event reports submitted to the Coordinating Center must be signed and dated by the participating site's Principal Investigator. Participating sites must use the SKCCC template for reporting adverse events per SKCCC policy. Information to be provided must include:

- Subject ID number, and initials
- Date of the event
- Description of the event
- Description of site's response to the event
- Assessment of the subject's condition
- Subject's status on the study (on study, off study, etc.)
- Attribution of event to study drug

Participating Sites

Participating sites are responsible for reporting adverse events to their IRB according to its specific requirements and to the Coordinating Center as follows:

Fatal Events whether anticipated or unanticipated, and whether or not related to the study must be reported to the Coordinating Center within **24 hours** of the participating site Principal Investigator's learning of the event.

Serious and Unanticipated Adverse Events as defined above must be reported to the Coordinating Center within 24 hours of the participating site Principal Investigator's learning of the event.

Other Serious Adverse Events which may result in a change to the protocol, informed consent, or risk to subjects as specified in the protocol must be reported within three (3) working days of the participating site Principal Investigator's learning of the event.

Adverse Events which result in no change to protocol, informed consent, or risk to subjects must be reported to the Coordinating Center on a monthly basis.

Adverse event reports are to be emailed to the Coordinating Center at . Follow-up reports are to be emailed to the Coordinating Center as necessary.

The investigator must also report follow-up information about SAEs within the same time frames.

If a non-serious AE becomes serious, this and other relevant follow-up information must also be provided within the same time frames described above.

All SAEs for Arm A patients must be collected whether or not they are considered causally related to the investigational product. Investigators and other site personnel are responsible for reporting all casually related SAEs to their IRB and the Protocol Chair.

All SAE's should be reported to the Coordinating Center by email at

Toxicity will be scored using CTCAE Version 4.0 for toxicity and adverse event reporting. A copy of the CTCAE Version 4.0 can be downloaded from the CTEP homepage

(http://ctep.info.nih.gov). All appropriate treatment areas should have access to a copy of the CTCAE Version 4.0. All adverse clinical experiences, whether observed by the investigator or reported by the subject, must be recorded, with details about the duration and intensity of each episode, the action taken with respect to the test drug, and the subject's outcome. The investigator must evaluate each adverse experience for its relationship to the test drug and for its seriousness. The investigator must appraise all abnormal laboratory results for their clinical significance. If any abnormal laboratory result is considered clinically significant, the investigator must provide details about the action taken with respect to the test drug and about the subject's outcome. Only clinically significant lab abnormalities will be recorded as adverse events.

6.2.1 Pregnancies

Pregnancy of a female subject or the female partner of a male subject occurring while the subject is on CC-486, or within 4 weeks after the subject's last dose of CC-486, are considered expedited reportable events. If the subject is on CC-486, it is to be discontinued immediately. The pregnancy must be reported to Celgene Drug Safety within 24 hours of the Investigator's knowledge of the pregnancy by phone and facsimile using the SAE Form. The female subject may be referred to an obstetrician-gynecologist (not necessarily one with reproductive toxicity experience) or another appropriate healthcare professional for further evaluation.

[figure not shown]
The Investigator will follow the pregnant female until completion of the pregnancy, and must notify Celgene Drug Safety of the outcome of the pregnancy (either normal or abnormal outcome) as specified below. The Investigator will provide this information as a follow-up to the initial SAE.

If the outcome of the pregnancy meets the criteria for immediate classification as a SAE (i.e., spontaneous abortion [any congenital anomaly detected in an aborted fetus is to be documented], stillbirth, neonatal death, or congenital anomaly), the Investigator should follow the procedures for Expedited Reporting of SAEs to Celgene (i.e., report the event to Celgene Drug Safety by facsimile within 24 hours of the Investigator's knowledge of the event).

All neonatal deaths that occur within 30 days of birth should be reported, without regard to causality, as SAEs. In addition, any infant death after 30 days that the Investigator suspects is related to the *in utero* exposure to CC-486 should also be reported. In the case of a live "normal" birth, Celgene Drug Safety should be advised as soon as the information is available.

If a female partner of a male subject taking CC-486 becomes pregnant, the male subject taking the project should notify the Investigator, and the pregnant partner should be advices to call their healthcare provider immediately.

6.2.2 Celgene Drug Safety Contact Information:

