- 14. Women of childbearing potential should be advised to avoid becoming pregnant and men should be advised to not father a child while receiving treatment with CC-486 or *nab*-paclitaxel. All men and women of childbearing potential must use effective methods of birth control throughout the study and for three months after completing treatment.
- 15. Women of childbearing potential must have a negative serum or urine β -hCG pregnancy test at screening.
- **16.** Subjects must have < Grade 2 pre-existing peripheral neuropathy (per CTCAE)

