5.5 Follow-up Phase Both Arms

No disease recurrence:

Less than 10% of patients who have undergone surgery will not develop tumor recurrence after adjuvant therapy.

Therefore, if patients have not recurred after one year of therapy with CC- 486 (Arm A) the drug will be discontinued.

Patients in Arm A will undergo a safety assessment 28 days (\pm 2 days) post the last dose of protocol therapy for resolution of toxicity.

Because Arm B patients do not receive study drug, a safety assessment will not be performed.

All patients (Arm A and B) will be then be contacted (ideally) every 3 months on to obtain the following information about recurrence, survival and anti-cancer treatment (2.2 Study Calendar):

- Any further therapy received (records to be obtained)
- Subjective response on therapy (records to be obtained)
- Any CA 19-9 drawn (records to be obtained)
- Any imaging (images to be obtained)

Disease recurrence

At the time of recurrence, Arm A and Arm B subjects will undergo biopsy of the recurrent lesion per the method determined best per the investigator.

Post recurrence images will be also obtained (pre-recurrence images are optional)

Thereafter, attempts to contact patients every 3 months in order to obtain lesion assessments/post recurrence images, CA19-9 and anticancer treatment and survival information as detailed in section 5.4.2. If study team is unable to make contact with patients, information may be obtained through medical and public records. This information will continue to be collected for patients until patients hit second disease progression.

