5.6 Concomitant Therapy

5.6.1 Recommended Concomitant Therapy

Subjects should receive full supportive care, including transfusions of blood and blood products, antibiotics, antiemetics, and growth factor support when appropriate.

- It is recommended that all subjects must be pre-medicated for nausea and vomiting prior to the administration of CC-486. Administration of a 5-HT3 serotonin receptor antagonist is recommended prior to CC-486. Antiemetics should be administered at least 30 minutes prior to administration of CC-486. Additional doses may be administered if required. Other antiemetic medications (prochlorperazine, lorazepam, etc.) may also be taken for delayed nausea as needed. Specific anti-emetic regimens are up to the discretion of the investigator.
- 2. Diarrhea: If diarrhea occurs during dosing, an antidiarrheal agent(s) may be used. It is recommended that patients experiencing diarrhea associated with CC-486 be managed according to the guidelines provided in Appendix C, which are based on a publication in

the Journal of Clinical Oncology⁴³. A dose reduction of CC-486 may be appropriate based on the severity of diarrhea observed and the response to treatment intervention.

3. Contraceptive Therapy: Sexually active men and women of child-bearing potential must agree to use effective contraception.

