6.3.1 Expedited reporting by investigator to Celgene

Serious adverse events (SAE) are defined above. The investigator must inform Celgene in writing using a Celgene SAE form or MEDWATCH 3500A form of any SAE within 24 hours of being aware of the event. The written report must be completed and supplied to Celgene by facsimile within 24 hours/1 business day. The initial report must be as complete as possible, including an assessment of the causal relationship between the event and the investigational product(s), if available. Information not available at the time of the initial report (e.g., an end date for the adverse event or laboratory values received after the report) must be documented on a follow-up report. A final report to document resolution of the SAE is required. The Celgene tracking number (OA-PANC-PI-0294) and the institutional protocol number should be included on SAE reports (or on the fax cover letter) sent to Celgene. A copy of the fax transmission confirmation of the SAE report to Celgene should be attached to the SAE and retained with the subject records.

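### The contraception, pregnancy-reporting and SAE sections set inconsistent post-treatment periods; partner pregnancies after week 4 have no clear reporting rule, and no scheduled contact asks about pregnancy

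*Combined protocol and SAP*

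**What the plan says.** Inclusion criterion 14 (section 5.2.1) states that men and women of childbearing potential "must use effective methods of birth control throughout the study and for three months after completing treatment". Section 5.6.1 repeats the duty without a duration: "Sexually active men and women of child-bearing potential must agree to use effective contraception".

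Section 6.2.1 covers "Pregnancy of a female subject or the female partner of a male subject occurring while the subject is on CC-486", and after treatment only a pregnancy "within 4 weeks after the subject's last dose of CC-486, are considered expedited reportable events". The same section tells the investigator to follow the pregnancy to its end and report the outcome. Its sentence on notification by a male subject is worded for a man who is on the drug.

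Section 6.1.1 lists pregnancy, and separately congenital anomaly or birth defect, among the serious adverse events, with no time limit. Section 6.2 requires all SAEs in Arm A to be collected whatever their cause. Section 6.3.1 requires the investigator to inform the drug supplier "of any SAE within 24 hours of being aware of the event", again with no post-treatment cut-off.

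On collection, section 5.5 says "Patients in Arm A will undergo a safety assessment 28 days" after the last dose, with a margin of 2 days. Later contacts, ideally every 3 months, are to "obtain the following information about recurrence, survival and anti-cancer treatment". The schedule in section 2.1 has pregnancy tests at screening and Cycle 1 only.

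**The concern.** A protocol that asks participants to avoid conception for three months after treatment would normally want to hear of a pregnancy that starts within those three months. Here the section written for pregnancies stops at 4 weeks, while the general safety sections do not stop at all. A site that learns of a pregnancy at week 8 gets two answers if the patient is the subject, and no clear answer if she is the partner of a male subject.

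What is at stake is the completeness of the drug's pregnancy-exposure record, including the outcome for the child. A rule that depends on the investigator's awareness is also only as good as the means of becoming aware, and none is written into the contacts after treatment.

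**Working it through.** The plan gives no figure on this point to reproduce. The check is a comparison of two windows, followed by a reading of which rule applies to whom.

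**1. Size of the mismatch**

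Inputs: contraception period C = three months after treatment (criterion 14); pregnancy-reporting window W = 4 weeks = 28 days after the last dose (section 6.2.1). Both are counted from the last dose.

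Share of the contraception period outside the window = (C − W) / C.

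| Three months counted as | C (days) | C − 28 | Share |
|---|---|---|---|
| Three 28-day months | 84 | 56 | 66.7% |
| Shortest three calendar months | 89 | 61 | 68.5% |
| 90 days | 90 | 62 | 68.9% |
| Average three months | 91.3 | 63.3 | 69.3% |
| Longest three calendar months | 92 | 64 | 69.6% |

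The result is 67% to 70% however months are counted. This is a share of calendar time, not of pregnancies missed.

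**2. Which rule applies in roughly weeks 5 to 13**

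| Case | Section 6.2.1 | Sections 6.1.1, 6.2 and 6.3.1 |
|---|---|---|
| Female subject, pregnancy begins in week 6 | Outside the window | An SAE; reportable within 24 hours of awareness, with a final report on resolution |
| Partner of a male subject, pregnancy begins in week 6 | Outside the window | Partners not named; SAE collection is framed around Arm A patients |
| Either, pregnancy begins on day 25 and is recognised on day 50 | Inside the window if occurrence means conception; the 24-hour clock starts at the investigator's knowledge | As above |

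For the female subject the sections conflict. For the partner there is no clear rule, either for the report or for following the outcome.

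**3. How the investigator would find out**

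- Pregnancy tests: screening and Cycle 1 only (section 2.1 and its note 12). The end-of-treatment list in section 5.4.1 has none.
- Safety assessment at 28 ± 2 days: adverse events are recorded, but no pregnancy question is listed. A conception late in the 4-week window would usually not yet be recognised.
- Follow-up contacts (sections 2.2 and 5.5): new therapies, response, CA 19-9, imaging and survival. Pregnancy is not listed.
- Male subjects: the duty to notify is written for men on the drug, so no sentence tells a man who has stopped to report a partner's pregnancy, even within the 4 weeks.

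**The case against.** A reader might infer that pregnancies after week 4 are simply not reportable, and that two thirds of a risk period goes uncaptured. The documents do not support that.

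- Section 6.1.1 makes pregnancy an SAE with no end date, section 6.2 requires all Arm A SAEs to be collected, and section 6.3.1 sends any SAE to the supplier. Read literally, a female subject's pregnancy in week 8 that the investigator learns of is reportable. This stands: for her the fault is contradiction, not absence.
- It would also go too far to say that fetal harm would go unreported. Congenital anomaly is itself an SAE, and the sentences in section 6.2.1 on neonatal and later infant deaths do not repeat the 4-week limit.
- Late recognition is not the same as non-reportability. A pregnancy that occurs inside the window and comes to light afterwards still has to be reported.
- Criterion 14 sets a contraception period and does not call it a risk period. It also names nab-paclitaxel, which this protocol does not assign, so the three months may not have been set for CC-486 alone. A precautionary contraception period and an expedited-reporting window can serve different purposes, and nothing in the documents says that they must be equal.
- A footnote to section 2.2 lets the study team ask for other information at the principal investigator's request. That permits a pregnancy question but does not plan one.

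These points narrow the concern but do not remove it. The general SAE rules do not clearly reach partners, they run from awareness that no scheduled contact is designed to produce, and the protocol gives no reason for the difference in periods.

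**Conclusion.** The sections on contraception, pregnancy reporting and SAEs are inconsistent on the post-treatment period and need to be reconciled. The gap between the contraception period and the pregnancy-section window is 67-70% of the former. It is firmest for partner pregnancies, which only section 6.2.1 names, and for detection, because nothing listed after Cycle 1 asks about or tests for pregnancy.

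The conclusion assumes that completing treatment in criterion 14 means the last dose, and that three months is the end of the requirement; a later end would widen the gap.

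The practical scale is small. At most 30 patients are to be assigned CC-486 (section 1.1). The documents give no expected number of pregnancies, so the statement that cases will be few is a judgement from that arm size. Sample size, power, the toxicity stopping guideline and the efficacy analyses are unaffected. No view is taken on what the contraception period should be.

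**What to change.** 1. Reconcile criterion 14 with sections 6.1.1, 6.2.1 and 6.3.1. The sponsor should confirm the post-treatment contraception period, check whether the reference to nab-paclitaxel belongs there, and state one reporting and outcome-follow-up window for subjects and partners that is not shorter than the confirmed period.
2. Extend the male subject's duty to notify in section 6.2.1 from the time on drug to the same window.
3. Add one question for Arm A, covering pregnancy in the subject or a partner, to the 28-day safety assessment (section 2.1) and to the first follow-up contact (section 2.2). That contact falls within 3 months of the safety assessment, so up to about 28 + 91 = 119 days after the last dose. Held near that limit, it would cover the whole of the present three months; held earlier, it would cover part.

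The cost is a text amendment, one question at contacts already scheduled, and possibly a few more reports. No new visit or test is needed.

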6.3 Investigator Reporting Responsibilities

The conduct of the study will comply with all FDA safety reporting requirements.

6.3.1 Expedited reporting by investigator to Celgene

Serious adverse events (SAE) are defined above. The investigator must inform Celgene in writing using a Celgene SAE form or MEDWATCH 3500A form of any SAE within 24 hours of being aware of the event. The written report must be completed and supplied to Celgene by facsimile within 24 hours/1 business day. The initial report must be as complete as possible, including an assessment of the causal relationship between the event and the investigational product(s), if available. Information not available at the time of the initial report (e.g., an end date for the adverse event or laboratory values received after the report) must be documented on a follow-up report. A final report to document resolution of the SAE is required. The Celgene tracking number (OA-PANC-PI-0294) and the institutional protocol number should be included on SAE reports (or on the fax cover letter) sent to Celgene. A copy of the fax transmission confirmation of the SAE report to Celgene should be attached to the SAE and retained with the subject records.

6.3.2 Report of Adverse Events to the Institutional Review Board

The principal Investigator is required to notify his/her Institutional Review Board (IRB) of a serious adverse event according to institutional policy.

6.3.3 Investigator Reporting to the FDA

Serious adverse events (SAEs) that are **unlisted/unexpected**, and at least possibly associated to **5-azacitadine**, and that have not previously been reported in the Investigator's brochure, or reference safety information document should be reported promptly to the Food and Drug Administration (FDA) by telephone or by fax by the IND sponsor. Fatal or life threatening SAEs that meet the criteria for reporting to the FDA must be reported to the FDA within 7 calendar days after awareness of the event. All other SAEs that meet the criteria for reporting to the FDA must be reported to t

A clear description of the suspected reaction should be provided along with an assessment as to whether the event is drug or disease related.

In accordance with the regulation 21 CFR § 312.33, the IND Sponsor shall within 60 days of the anniversary date that the IND went into effect submit a brief report of the adverse events and progress of the investigation. Please refer to Code of Federal Regulations, 21 CFR § 312.33 for a list of the elements required for the annual report. All IND annual reports will be submitted to the FDA by the IND Sponsor.

6.4 Adverse event updates/IND safety reports

Celgene shall notify the Investigator via an IND Safety Report of the following information:

- Any AE associated with the use of drug in this study or in other studies that is both serious and unexpected.
- Any finding from tests in laboratory animals that suggests a significant risk for human subjects including reports of mutagenicity, teratogenicity, or carcinogenicity.

The Investigator shall notify his/her IRB/EC promptly of these new serious and unexpected AE(s) or significant risks to subjects.

The Investigator must keep copies of all AE information, including correspondence with Celgene and the IRB/EC, on file (see Section 12.4 for records retention information).

7 Radiologic Evaluation

